### **Figure 5**. EHR message linked to decision support alert

**Call Documentation** 

[name], MD at 1/11/2016 9:32 AM

Status: Signed Editor: [name], MD (Physician)
Sent on behalf of [name] (President, CMI-UPMC) and [name] (Division Chief, Renal-Electrolyte Division, University of Pittsburgh)

CMI has partnered with our nephrology division to improve the care of our patients with CKD. Your patient has been identified as high risk to progress to ESRD and may be in need of nephrology input.

Our program will allow you and your patient to receive timely input to help improve the life of kidneys and to make sure the complications of renal disease are being monitored and addressed, i.e., blood pressure control, need for fistula, etc.

Your patient will be seeing you in the next few days. There are 3 options we offer you:

- Allow us to do an eConsult prior to the visit. This is a new service which we are piloting on a limited basis where a nephrologist will review the chart and make recommendations to you. This may be particularly useful if you are not sure that face-to-face consultation is needed (currently no charge to the patient).
- Refer to a nephrologist when you see the patient at her upcoming office visit.
- Choose "No Consult" option, if you do not think any of the above actions are warranted. Please also provide us a reason for this choice.

Please go to the BestPractice section on the Visit Navigator to record your response We look forward to helping you care for this patient.

If the care bundle is ordered, a nephrologist will review the chart and provide specific prior to the appointment. In addition, a telephonic appointment with a pharmacist will be made and s/he will contact the patient and review their medication list and provide safety recommendations to the PCP through the EHR.

During the patient visit, a real time decision support alert will remind the PCP to review the nephrology e- consult and pharmacist recommendations, to inform the patient about their CKD status, and to refer the patient for complimentary CKD education. Following the visit, the patient will have their CKD education sessions scheduled. Subsequent nephrology electronic follow-ups will be scheduled according to the patient's clinical needs (generally every 3-6 months) and coordinated through the PHM dashboard. The intervention has been refined to facilitate care enhancements, preserve workflow, and minimize PCP and patient burden.

We have also taken steps to enhance PCP acceptance of the intervention: a) high-level support from UPMC Health Plan, PCP network (Community Medicine Incorporated, including 90 practices and 330 PCPs), and the Nephrology Division; b) meeting with lead physicians and refining the intervention to harmonize with workflow; c) documenting PCP responses in the EHR; d) ongoing communication with PCP groups and leadership.

Electronic nephrology consult. Orders for e-consults will be received in an electronic basket monitored by the study coordinator. The consults will be routed to 1 of 12 board certified nephrology clinicians, who will undergo training to standardize consult focus and communication. The notes will adopt a "Situation, Background, Assessment, Recommendation"94-97 template to ensure clear, concise communication. The note will be completed at least several days prior to the patient's appointment and routed to the PCP's message basket and documented in the chart to allow time for review and clarification. The initial consult will focus primarily on HTN control, proteinuria assessment and suppression, RAASi use, and medication safety. The note will include a bolded list of recommendations with orders placed in a pended status (i.e., entered, but awaiting acceptance from the PCP). To enhance communication and care coordination, the e-consultant will ensure CKD is added to the problem list. 98 In addition, the problem list will convey that the patient is followed by the e-consult team, reachable via listed message baskets and phone numbers. The nephrologist will include an order for remote electronic follow-up, which will be captured in the PHM dashboard. Electronic messages will be sent to the nephrologist to perform the follow-up approximately 3 weeks before the recommended interval. When necessary, traditional office evaluations will be suggested.

Medication reconciliation and safety review. Prior to their upcoming PCP appointment, patients will be contacted to schedule a remote medication review with a study pharmacist (PharmD) who has expertise in medication therapy management. Appointment availability will include evenings to maximize patient convenience. Patients will be asked to have their medications available for the review. Prior to and during the review, the PharmD will gather clinical data from the EHR's active and recently discontinued medications. S/he will also note the patient's most recent medication dispensing record for each medication (usually documented in the EHR with electronic scripts). The study pharmacist will assess the patient's self- reported medication regimen, administration routine, adherence, and will reconcile this with the medication information contained in the EHR. S/he will assess over the counter (OTC) medications and herbal products, will deliver guidance on OTC medications to avoid, and will screen for possible adverse effects of all medications. [name], [name], PhD (Co-I), will guide the medication review, perform intermittent audits to ensure intervention fidelity, and direct additional staff training if necessary.

The pharmacist will document their findings in the EHR using a standard medication reconciliation and review template. The note will be sent to the PCP's EHR inbox. Specific, concise recommendations and reasoning will be listed at the top of the note. Thereafter, pharmacist medication reviews will be scheduled quarterly.

Standardized patient education. Once an order for CKD education is placed, the research team will schedule individual or group education session. Caregivers will be encouraged to attend. Study nurse educators will deliver the CKD education. New nurse educators will undergo an intensive 3- to 6-month training period under the guidance of the PIs and existing UPMC CKD nurse educators and dietitians. Simulated and authentic patient education sessions will be observed to judge readiness.

Print and video based education material from the National Kidney Disease Education Program (NKDEP) and the National Kidney Foundation that reviews the role of the kidneys, CKD risk factors, dietary guidelines, pharmacotherapy, medication adherence and safety, frequently asked questions, and dialysis modalities will be used. The nurse will document

the session in the EHR using a brief templated education note (that is captured by the PHM dashboard), and route it to the PCP and nephrologist. After the initial sessions, annual refresher sessions will be scheduled.

### Multi-disciplinary Case Discussions

Prior to providing recommendations to PCPs, every patient's management will be discussed in case conference calls (2-4 times per week) attended by APPs, nephrologists, and pharmacists, to arrive at consensual individualized recommendations for patients.

### Intervention Fidelity

All nephrologists, nurse educators, and PharmDs delivering a component of the intervention will undergo standardized training until they achieve consistent and acceptable performance. This will include review of concise educational materials, observation and apprenticeship with existing providers at the local site, the use of checklists operationalizing key aspects of each intervention, the use of SBAR (situation, background, assessment, recommendation) EHR templates, 94-97 and direct observation during role played and actual interventions. After initial implementation, the study/site PIs will randomly audit 5-10% of e- consults every 3 months. [name] will randomly audit 5-10% of pharmacy communications every 3 months. Providers will receive targeted feedback based on findings. Providers will also continue to use checklists to document completion of key aspects of the intervention as well as deviations throughout the study. Refreshers will occur every 6-12 months and remediation will occur as dictated by observed performance (i.e., <80% fidelity with items on checklist).

### V. Data collection and Outcomes

Routinely collected EHR and administrative data will be abstracted for outcomes assessment as shown in Table 2. PCP practice level data will be obtained from public records.

Table 2: Key variables and covariates for usual care and intervention patients

Variables	Variable descriptions	Data source details
Renal function and rate of change in renal function	
 
Baseline serum creatinine – most recent creatinine from date of study enrollment visit with PCP up to 365 days prior to the visit.
 
Baseline eGFR – Calculated using CKD-EPI.
 
Baseline rates of change in eGFR - determined from baseline eGFR and prior eGFRs between 365 to 730 days before the baseline value.
 
	EHR (restricted to outpatient labs)
Socio- demographics	
 
Age, gender, race, ethnicity, marital status, insurance, and zip code for linkage with neighborhood median household income.
 
Baseline values defined on the date of baseline visit
 
	EHR
Comorbid conditions	
 
DM, HTN, hyperlipidemia, CAD, cerebrovascular disease, peripheral vascular disease, CHF, arrhythmia, gout, chronic lung disease, chronic liver disease, mood disorder, and malignancy.
 
Baseline values defined on the date of baseline visit and using a 24 month "look back" period.
 
	Phenotypes using administrative & clinical codes, meds, & lab values validated in local EHR. 12,38,39
Blood Pressure	
 
Baseline BP - mean outpatient BP from the date of the baseline study visit with the PCP until 180 days prior to the baseline visit.
 
Follow-up BP - all outpatient BPs after patient enrollment
 
	Office visit vital signs recorded in the EHR
Medication use	tion  • RAASi, NSAID and other medications deemed a potential safety concern (e.g., allopurinol, gemfibrozil, glyburide, metformin, etc.)  • Medication related problems and drug record discrepancies	
Laboratory values		
Urine albuminuria	
 
Quantitative urine albuminuria - most recent ACR from the baseline visit up to 365 days prior to the visit.
 
Urine dipstick albuminuria - median of outpatient values available from the date of baseline visit up to 365 days prior to the visit.
 
	Outpatient lab values from EHR

### **Primary Outcome**

A ≥40% decline in eGFR or ESRD. 92 eGFR decline will be adjudicated based on the baseline creatinine and eGFR determined from the CKD-EPI equation and measured routinely in clinical practice. 99 ESRD will be defined as an eGFR < 10ml/min to account for patients with markedly reduced baseline eGFR values (i.e., 16-20ml/min).

The 40% decline surrogate outcome may increase power and precision by capturing additional events while maintaining a similar risk of type I error compared to the standard doubling of serum creatinine outcome. To limit surveillance bias, we will use 6-month ascertainment windows and average all values within each window. Our data indicate 75% of high-risk patients have an outpatient eGFR value every 6-months. Additional analyses will compare changes in eGFR slope over time (using splines to account for non-linearity.

### Secondary outcomes - Process of care outcomes

1. HTN control. Outpatient, sitting BP values measured during each outpatient encounter and recorded in the EHR. BP will be treated as a continuous variable. To minimize

- ascertainment bias, we will use 6-month ascertainment windows to determine an average BP for each patient for each 6-mo period. Patients lacking an outpatient value will have their last value carried forward
- 2. Use of RAASi. Will be determined by active use of an ACEi or ARB based on the EHR medication list at each outpatient encounter. Analyses will compare cumulative person-time exposure during the study.
- 3. Medication safety. We will examine the rates of use of several high-risk medications that can be associated with adverse outcomes in progressive CKD. Medication exposure will be determined by presence of the specified medication on the patient's EHR medication list at each outpatient encounter. Analyses will compare cumulative person-time exposure during the study.
  - a. Use of NSAIDs: use examined for all study patients
  - b. Use of glyburide: use examined for all diabetic study patients
  - c. Use of metformin: use examined for diabetic study patients with eGFR<30
  - d. Use of gemfibrozil: use examined for all study patients with eGFR<30.

Exploratory outcomes. Mortality, hyperkalemia, and health utilization (i.e., costs) including hospitalizations, emergency department visits, and outpatient encounters will be ascertained by a combination of EHR and administrative data from the UPMC health plan. The accessibility of administrative data that captures events outside the health system and supplements the EHR is a unique and complementary resource that will be leveraged in future study analyses.

### Adverse events

While it is unlikely that systematically providing evidence-based recommendations to PCPs of high-risk CKD patients by trained nephrologists and pharmacists will worsen overall clinical outcomes, we will monitor safety signals through the EHR, including hyperkalemia, ER visits, hospitalizations and mortality.

### VI. Regulatory and Oversight Considerations

This study meets the criteria for human subject's research.

We will conduct a cluster RCT of PCP practices, implementing a multifaceted PHM intervention for patients with high-risk CKD. The intervention targets improvements in the delivery of evidence-based care and outcomes. Patients with high-risk CKD will be identified through demographics and laboratory tests that are collected for clinical purposes. The PHM dashboard, which includes estimates from validated risk prediction models and eGFR trajectories, will be used to identify and track enrolled patients. Shortly before their regularly scheduled visit with an enrolled patient, PCPs randomized to the intervention arm will receive a decision support message and subsequent reminders notifying the provider of the patient's high-risk CKD status and recommending the following bundle: 1) an order for electronic nephrology guidance or formal nephrology office consultation if preferred; 2) medication therapy management by a PharmD, specifically including a medication reconciliation and safety review, and 3) CKD patient education. These interventions are all consistent with standard of care practices for patients with high-risk CKD and the PCP will always be permitted to accept or refuse these suggestions according to their clinical judgement. If the provider accepts these suggestions, the individual intervention components will be ordered, scheduled, coordinated, and tracked. If the provider refuses any of the components, they will be able to justify why their reasons for refusal. Refusal responses will be randomly audited to ensure accuracy.

### a. Recruitment and Informed Consent:

We will include all primary care providers at UPMC with an active primary care continuity clinic. We will identify these providers through provider rosters given to us by the respective departments and practices. We will maintain contact with each practice through biannual sessions held during their regular practice meetings or lunch meetings held at their offices. We will remind providers of the aims of the study and the intervention. We will also seek regular feedback from providers to identify unforeseen issues that were not encountered during the pilot study and will work collaboratively with them to identify suitable solutions. We will survey providers on their experience with the intervention using both multiple choice and open-ended questions. We will also collect feedback from them using standardized, templated forms during planned meetings. The study's PIs and nurses will meet with the practices as described above.

Per the University of Pittsburgh IRB and UPMC Quality Improvement committee guidance, the study will not require consent from PCP or patient to enroll them in the study. Both PCP and patients will be given information about the study and an opportunity to opt-out. We will continue to meet with PCPs to understand barriers that may arise and to develop solutions that ensure PCP burden is minimized and workflow is preserved.

Notably, all practicing PCPs who partake in this study are licensed providers. They vary in age from approximately 30 years to >60 years. All PCPs from UPMC primary care practices are included in this research; no one is excluded. The PCPs care for approximately 480,000 patients annually, including ~10,000 patients with high-risk CKD. Individual patients seen will vary greatly in age and health status as expected in any large group PCP practice.

The intervention will only target patients who have high-risk CKD using validated risk prediction models. Low- risk patients will be excluded because outcomes occur at a lower rate in this setting. Including these patients would necessitate a larger, longer, and costlier study to ensure adequate power to detect small but meaningful differences. Alternatively,

including these patients using the current study size and follow-up would result in an underpowered trial with significant potential for a type II error. Patients > 85 years of age will be excluded as best practices for CKD treatment are less clear in the very aged. Patients < 18 years will also be excluded (see inclusion of children below). Patients with a history of renal transplant, end-stage renal disease, or already under the care of a nephrologist will be excluded because these patients are generally receiving specialized care in addition to their PCP's care. In addition, patients with very limited prognoses (e.g., metastatic cancer, COPD on continuous oxygen, stage IV heart failure) will be excluded *during the screening process* due to the difficulty of substantially altering their course with CKD treatment enhancements.

Patients that are pregnant or prisoners will be excluded from the study if they are seen by a participating PCP during the study enrollment period. Evidence-based CKD care differs during pregnancy (e.g., contraindication of RAASi, different BP goals) and pregnancy and peripartum course are known to affect eGFR and albuminuria thereby uniquely affecting potential outcomes. In addition, because 2 components of our intervention bundle require scheduling a group CKD education session and a telephonic medication reconciliation and safety review with a PharmD, enrolling incarcerated patients would be impracticable.

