# I. Study Summary Synopsis

Title	Kidney C oordinated H e A lth M anagement P artnership (Kidney CHAMP) trial		
Short Title	K CHAMP Trial		
Study Description	This is a randomized clinical trial to test the effectiveness of a multifaceted EHR-based PHM intervention to improve evidence-based CKD care in high-risk patients		
Objectives	Primary Objective To perform a 42-month pragmatic, cluster RCT comparing the effect of an EHR-based PHM intervention versus usual care on key processes of care in 1,650 high-risk CKD patients.  Aim 1a: To examine the effect of the intervention on systolic blood pressure (SBP) in HTN patients.  Aim 1b: To examine the effect of the intervention on RAASi use in albuminuric patients.  Aim 1c: To examine the effect of the intervention on exposures to potentially unsafe medications.		
	Secondary Objective To test the clinical effectiveness of a multifaceted PHM intervention in reducing kidney disease progression in 1,700 high-risk CKD patients enrolled in a 42-month pragmatic, cluster RCT		
Primary Outcome	≥40% decline in estimated glomerular filtration rate (eGFR) or end stage kidney disease		
Secondary Outcomes	
 
blood pressure control
 
renin-angiotensin aldosterone system inhibitors use
 
exposure to potentially unsafe medications
 
		
Study Population	1,650 high-risk CKD patients not presently seeing a nephrologist		
Phase or Trial Type	Effectiveness		
Description of Sites/Facilities Enrolling Participants	100 University of Pittsburgh Medical Center (UPMC)-affiliated PCP practices located across southwest Pennsylvania University of Pittsburgh; University of Pennsylvania		
Description of Study	Intervention bundle includes nephrology electronic consults, pharmacist-led medication reviews and nurse-led CKD education		
Intervention	Usual Care: per PCP as routine		

Study Duration	42 months
Participant Duration	24 months

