### IV. Study Design

Study design. A 42-month cluster RCT with randomization occurring at the practice level (to minimize contamination) and stratified by number of high-risk CKD patients in the practice. All 90 practices will be randomized. Patient enrollment will continue for 18 months, with a minimum of 24 months of follow-up (**Fig 3**).

[figure not shown]

Figure 3. Flow diagram of cluster RCT of EHR-based PHM.

PCP primary care provider, PHM population health management, KFRE kidney failure risk equation, CA cancer

Population and Setting. The study leverages a PCP network that includes 90 practices; 330 PCPs; and over 480,000 patients to conduct a cluster RCT testing the effectiveness of an EHR-based CKD PHM intervention. In this pragmatic study, practices will be randomized to the intervention. Secondarily, their high- risk CKD patients who are not seeing a nephrologist will be enrolled.

Eligibility. Inclusion criteria are (**Figure 3**): a) age  $\geq$  18 and  $\leq$ 85, b) most recent eGFR < 60 ml/min/yr,c) UPMC health plan insurance, d) established care with UPMC PCP, e) high-risk CKD (see **Table 1**). Exclusion criteria are: a) history of kidney transplant, b) receiving maintenance dialysis, c) recent (within 12 months) outpatient nephrology visit, d) baseline eGFR  $\leq$  15ml/min, or e) expected survival  $\leq$  6 months/hospice.We will use the validated 4- variable KFRE to estimate 5-year ESRD risk. We will supplement these criteria by including other patients who are high risk for poor outcomes (**Table 1**).

Table 1: High risk CKD

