### PCP Recruitment and Engagement.

Before implementation at each site, we will provide a remote/on-site presentation during a scheduled practice meeting. Communication with lead physicians will continue during the study at least biannually by teleconference or on-site lunches to discuss feedback and concerns and document comments on a standardized feedback form. Study/Site PIs will also meet with practice physicians as needed to address concerns. We will anonymously survey intervention arm PCPs every 6 months to assess their experience with the intervention bundle. This will include: ease of use, questions communicated by patients, effects on patient medication use and adherence, utility of the recommendations, and temporal burden of the intervention. Minor adjustments to PHM intervention workflow will be made as needed to ensure continued workflow optimization.

[figure not shown]
Randomization. The unit of randomization will be the practice (**Fig. 3**), stratified by estimated number of eligible CKD patients within the practice (small [<15 patients], medium/large [≥15 patients]). Randomization will use a computer generated random number sequence with random block sizes of 4 and 6.

CKD Registry and PHM Dashboard. Our CKD registry includes all outpatients with a recent eGFR < 60 ml/min followed by a UPMC PCP. The CKD registry identifies patients with CKD, phenotypically characterizes them, and stores information on labs, medications of interest, upcoming PCP appointments, and information about CKD outreach (including dates of electronic outreach, medication reviews, patient education, and pending labs/studies). The registry is updated automatically with activity in the patient chart.

Dashboards are medical informatics data representations that can be employed when decisions need to be made about a population of patients. These tools display groups of patients based on clinical characteristics and allow providers to stratify, filter, and sort by relevant variables. Thus, subgroups of patients can be rapidly identified and targeted for more intensive therapy. Dashboards can improve evidence-based care; however, they have been slow to enter clinical

practice because of the sophisticated underlying data requirements.84,93

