Our CKD PHM dashboard (**Figure 4**) includes population-based reports built off of the registry (e.g., high-risk patients with PCP appointment in October), as well as graphical and tabular displays of key metrics (e.g.,identified subpopulation with albuminuria who are not on RAASi). Population reports accessible through the dashboard will allow the study coordinator to sort patients based on phenotypic data and upcoming PCP appointments, and include filters such as CKD stage, RAASi use, and PCP group. Longitudinal tracking and notation functions interface with the dashboard and allow documentation of study inclusion, and dates of scheduled/completed aspects of the intervention. Dashboard reports will allow the coordinator to rapidly flag patients for urgent concerns, send routine reminders to PCPs to implement recommended interventions, ensure follow-up on pending components of the intervention, and actively monitor follow-up status. Dashboard reports will be actionable and will allow the manager to view more detailed information in a viewing pane without leaving the report. The reports allow the coordinator to jump directly into activities to communicate with the patient, the patient's PCP, and the respective nephrologist or pharmacist.

Patient screening and enrollment. Each month, the coordinator will use the CKD PHM tool to review high-risk patients with an upcoming (within 1 month) appointment with their PCP to determine eligibility. Possible decisions will include actively enroll, permanently exclude, or not presently eligible but may rescreen if deemed high-risk at next PCP appointment. Once delineated, the patient's status is noted in the EHR with a modifiable study flag not visible to providers, but that is continually tracked, updated, and ascertained through the PHM dashboard.

For intervention patients, the coordinator will send a scripted EHR message with associated decision support to the PCP about 1-3 weeks prior to their scheduled PCP appointment. When the PCP accepts the decision support recommendations for an electronic nephrology consultation, a medication reconciliation and safety review, and standardized patient

education, the orders will be placed . Patients enrolled to practices randomized to usual care will receive care as they currently do.

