### **Final Statistical Analysis Plan**

Clinical outcome (primary study outcome): A ≥40% decline in eGFR or ESRD.(1) eGFR decline will be adjudicated based on the baseline creatinine and eGFR determined from the CKD-EPI creatinine (2021) equation.(6). To limit ascertainment bias, we will also use a once yearly decision support alert to remind

study PCPs in both arms to order a BMP on study patients, if results are not available in the last 6 months. ESRD will be defined as an eGFR < 10ml/min to account for patients with markedly reduced baseline eGFR values (i.e., 16-20ml/min). To limit surveillance bias, in addition to the above alert, we will use 6-month ascertainment windows and average all values within each window. (Table 1). Researchers involved in outcome assessment will be strictly blinded.

Process of care outcomes (secondary outcomes): 1) HTN control. Outpatient, sitting BP values measured during each outpatient encounter and recorded in the EHR. BP will be treated as a continuous variable. To minimize ascertainment bias, we will use 6-month ascertainment windows to determine an average BP for each patient for each 6-mo period. 2) Use of RAASi. Will be determined by active use of an ACEi or ARB based on the EHR medication list at each outpatient encounter. Analyses will compare cumulative person-time exposure during the study. 3) Medication safety. We will examine the rates of use of several high-risk medications that can be associated with adverse outcomes in progressive CKD. Medication exposure will be determined by presence of the specified medication on the patient's EHR medication list at each outpatient encounter. Analyses will compare cumulative person-time exposure during the study. a) Use of NSAIDs: use examined for all study patients, b) Use of glyburide: use examined for all diabetic study patients, c) Use of metformin: use examined for diabetic study patients with eGFR<30.

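### As worded, the twice-yearly practice sessions about the study and its intervention also reach usual-care practices, which conflicts with randomising by practice to limit contamination and with a routine-care comparator

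*Combined protocol and SAP*

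**What the plan says.** The comparator is described twice as ordinary care. The synopsis has "Usual Care: per PCP as routine". The screening and enrolment paragraph of Section IV has "Patients enrolled to practices randomized to usual care will receive care as they currently do". Section IV also gives the reason for the unit of allocation: "randomization occurring at the practice level (to minimize contamination".

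Section VI, Recruitment and Informed Consent, includes every UPMC primary care provider and then says: "We will maintain contact with each practice through biannual sessions held during their regular practice meetings or lunch meetings held at their offices". The next sentence reads: "We will remind providers of the aims of the study and the intervention". Neither sentence names an arm. PCP Recruitment and Engagement, in Section IV, plans contact with lead physicians at least twice a year, again without naming an arm. The same paragraph does limit the questionnaire: "We will anonymously survey intervention arm PCPs every 6 months". The opening of Section VI confines the high-risk message, the reminders and the bundle offer to intervention PCPs.

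Separately, both the original and the final SAP plan a once-yearly alert to remind "study PCPs in both arms to order a BMP on study patients, if results are not available in the last 6 months". The protocol's Primary Outcome text in Section V does not mention this alert.

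**The concern.** Cluster randomisation stops spill-over between colleagues and patients within a practice. It gives no protection against contact that the study team itself starts. Aim 1 names systolic pressure, RAASi use in albuminuric patients and exposure to potentially unsafe medications, and these are also the secondary outcomes. A session that reminds usual-care PCPs of the aims and the intervention therefore tells the control arm which behaviours are being measured and promoted.

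If some of those PCPs respond, the control arm moves toward the intervention arm. The process outcomes would be affected first, and the kidney outcome possibly through them. The Sample Size paragraph has no allowance for this. A null or small result would then be harder to read as a comparison with routine care.

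**Working it through.** **1. Which activities are limited by arm?**

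| Activity | Where | Arm as written |
|---|---|---|
| High-risk message, reminders, bundle offer | VI, opening | Intervention only |
| PCP survey | IV, PCP Recruitment and Engagement | Intervention only |
| PCP survey, described again | VI, Recruitment and Informed Consent | None stated |
| Presentation before implementation | IV, PCP Recruitment and Engagement | None stated; tied to implementation at a site |
| Lead-physician contact | IV, PCP Recruitment and Engagement | None stated |
| Biannual sessions with reminders of aims and intervention | VI, Recruitment and Informed Consent | Each practice |
| Yearly BMP alert | SAP, Clinical outcome | Both, explicitly |

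The authors limit by arm in some places, and the sessions carry no limit. The survey rows show that Section VI also drops a limit that Section IV states, so the wording alone does not settle what was intended.

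**2. Exposure if followed literally.** Two sessions a year over a 42-month study is 42/6 = 7 sessions per usual-care practice.

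**3. The plan's sample size.** Inputs from the Sample Size paragraph: 1,102 under individual randomisation, ICC 0.01, cluster size 19, attrition 20%.

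- Design effect = 1 + (19 − 1) × 0.01 = 1.18.
- 1,102 × 1.18 / 0.80 = 1,626, about 1.7% below the stated 1,653. A design effect of 1.20 gives 1,653 exactly.

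The figure is reproduced closely, and no term in it covers contamination.

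**4. Illustration of a loss of contrast.** The documents give no size, so let d be an assumed fraction of the log hazard ratio that is lost because control moves toward intervention: HR_d = 0.64^(1 − d). Allocation is assumed 1:1.

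- *Basis A, power taken as exactly the stated 80% minimum:* power = Φ[(1.960 + 0.842)(1 − d) − 1.960]. The total needed to restore 80% is 1,653/(1 − d)².
- *Basis B, the SAP's 18 months of accrual plus 24 months of follow-up:* effective N = 1,653 × 0.80 / 1.18 = 1,121, with constant hazards, control hazard −ln(0.85)/24 per month and uniform accrual. Undiluted event proportions are 0.1998 and 0.133, giving 186.5 events. Power = Φ(0.446 × √186.5 / 2 − 1.96) = Φ(1.09) = 86%.
- *Basis C, as B but counting only 24 months per patient:* proportions 0.15 and 0.0988, 139.4 events, power 75%.

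| Assumed d | HR_d | Power, A | Power, B | Power, C | N for 80%, A |
|---|---|---|---|---|---|
| 0 | 0.640 | 80% | 86% | 75% | 1,653 |
| 5% | 0.654 | 76% | 82% | 70% | 1,832 |
| 10% | 0.669 | 71% | 77% | 65% | 2,041 |
| 20% | 0.700 | 61% | 66% | 54% | 2,583 |
| 30% | 0.732 | 50% | 54% | 43% | 3,373 |

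The table shows how sensitive power is to d. It does not estimate d.

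**The case against.** The strongest reply is that the recruitment section is loosely written and means intervention practices. Its content is feedback on the intervention, issues not met in the pilot, and workflow, which suits practices that run the programme. It repeats the survey without the arm limit given in Section IV. The Potential Risk text likewise speaks of messages to PCPs in general, although the opening of Section VI sends them to one arm. This reply has force: the documents do not show that usual-care practices were briefed. It does not remove the need to say so, because the sentence as it stands covers each practice.

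A reader might go further in four ways, none of which the documents support.

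- *That the protocol promises usual care no contact.* It does not. The conflict is with its general descriptions of routine, unchanged care and with its stated reason for randomising by practice.
- *That the contrast is diluted by a known amount.* No bundle component is offered to usual care, and nothing in the documents supports 10%, 20% or 30%. Potential Risk calls usual care, including continuing education for PCPs, ineffective, which points to a small effect.
- *That the BMP alert contaminates the comparator or unmasks enrolment.* The alert is a deliberate measure against ascertainment bias, applies to both arms and, as described, carries no treatment advice. If it fires more often in the less-tested arm, that is how it evens out eGFR capture. The screening paragraph describes "a modifiable study flag not visible to providers", but whether the alert reveals study status depends on wording that the documents do not give.
- *That the 3 mmHg SBP difference would shrink in proportion.* That figure is a detectable difference, not a predicted effect.

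**Conclusion.** The point stands as a conflict in the text and an avoidable risk. As written, the biannual sessions take the study's aims and intervention to usual-care practices, up to 7 times each. That is inconsistent with limiting contamination by design and with a comparator of unchanged care. The both-arm alert is sound in purpose, but it is missing from the protocol's outcome section and from the description of usual care.

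Any bias from briefing usual-care PCPs would most plausibly be toward the null. Its size is unknown and could be zero. The power losses above hold only under the assumed d, 1:1 allocation, proportional constant hazards and attrition no greater than the planned 20%. They do not show that the trial is underpowered or that a null result could not be interpreted.

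**What to change.** - In PCP Recruitment and Engagement and in Recruitment and Informed Consent, limit the sessions, intervention reminders and feedback meetings to intervention practices. Give usual-care practices only the neutral study and opt-out notice.
- Keep the BMP alert in both arms, worded as a generic overdue-lab reminder. Add it to the Primary Outcome text in Section V.
- Describe the comparator in the synopsis and in Section IV as usual care plus a yearly overdue-BMP reminder.
- Report study contacts per practice and alerts fired per patient, by arm.

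The final SAP gives 31 July 2022 as study end and March 2023 as first disclosure of results. If conduct is complete, what remains is to report which usual-care practices received sessions and what was covered, and to interpret the contrast accordingly.

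The cost is wording, simple counts and fewer meetings. Control outcomes come from the EHR, so less contact should not affect their collection. The downsides are less engagement with usual-care practices and a slightly less clean comparator label.
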